Study Protocol and Statistical Analysis Plan:

Our study was designed as prospective cohort study. 65 women between the ages of 18-52 who applied to the Istanbul Medical Faculty Gynecology and Infertility departments due pelvic pain, infertility or abnormal bleeding between October 2018-October 2021 were included in the study. As a result of their gynecological examination and transvaginal ultrasonography results, these women were divided into adenomyosis (n=34) and fibroids (n=31) groups. Women with a history of malignancy, oral contraceptive use, hormonal intrauterine device users or women using gonadotropin-releasing hormone agonists were not included in the study. Ethical committee approval was given and informed consents were obtained from the patients before the examination.

The definitive diagnosis of patients with suspected adenomyosis and fibroids according to transvaginal ultrasound examination was confirmed by intravenous contrast-enhanced pelvic MRI. Thus the reference method used for confirmation was MRI. Magnetic resonance imaging was evaluated by a separate radiology specialist with 17 years of experience in pelvic MRI. If the junctional zone was observed to be thicker than 1.2 cm in magnetic resonance imaging, or the difference between the maximum and minimum measurement values taken from the junctional zone was more than 0.5 cm, adenomyosis diagnosis was established. Focal lesions with clear borders in the uterus were interpreted in favor of myoma uteri. (1)

In the study group, detailed anamnesis was taken from the patients, their menstrual cycles, body mass indexes, current drug use, family history, and smoking habit were questioned. The patients included in the study (adenomyosis group) and control group (fibroid group) were examined with both transvaginal ultrasound and transvaginal elastography devices.

Siemens Acuson X600 EV9F10 endovaginal ultrasound with 3-9 MHz frequency and 180 degree viewing angle probe was preferred for transvaginal ultrasound examination. Canon Applio i800 11C3 endovaginal ultrasound with 3-11 MHz frequency and 180 degree viewing angle probe was used for elastography examination.

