Elastography data of the study and control groups were compared. Shear wave elastography was used with a transvaginal transducer providing a clear image up to 3 cm depth. No additional pressure or compression was applied to the transvaginal probe during the procedure. Minimum pressure was applied to the cervix for imaging and the probe was held still for approximately 2-5 seconds to obtain a fixed, stable image of the imaging field which contains the pathological lesion. The technique implemented in our study was adopted from the literature published by Mitkov et al. (2)(3)

Transvaginal gray scale ultrasound was performed in B-Mode by a gynecologist with at least 10 years of gynecological ultrasonography experience. In the study group, the presence/absence of hypoechoic areas, anechoic pools, asymmetric uterine growth, global uterine enlargement, deletion of the endo-myometrial zone, subendometrial thickening, global uterine growth, and linear shadows extending in the form of fans in the myometrium were recorded. Then, patients listed in study group were evaluated with elastography, and the hardness of the existing lesions was expressed in Young's modulus and recorded as elastographic data. Sonoelastography imaging was performed by an expert radiologist with 20 years of transabdominal/transvaginal ultrasonography and 7 years of sonoelastography experience.

To measure tissue stiffness in shear-wave elastography, Young's modulus, whose unit is kilopascal (kPa), was used in gynecological mode, with an upper limit of 180 kPa. Numerical values of Young's modulus were measured in areas with maximum myometrial stiffness for the respective pathologies. (Adenomyosis/Fibroid) Measurements were recorded on images in which the color window containing the lesion was completely stained and shear waves were completely set with equal distances over the pathological lesion in shear wave elastography. Tissue stiffness of the examined area was visualized with a color map in real-time mode. Harder tissues with high kPa values are mapped in red, green and yellow colors, while relatively soft tissues with lower kPa values are indicated in blue-violet colors. Evaluation of tissue stiffness was made in selected regions of interest with round-shaped circles adjustable up to 10 mm in diameter. All images and data were saved in the memory of the ultrasound device for further evaluation and processing. The

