numerical values which represent the mean stiffness value of the region of interest; were set automatically in terms of kilopascal according to Young's Modulus by the device. These mean stiffness values were defined, and the minimum and maximum mean stiffness values were recorded for both study and control groups.

While evaluating the findings, IBM SPSS Statistics 22 program was used for statistical analysis. The conformity of the parameters to the normal distribution was evaluated with the Shapiro Wilks test. During the assessment of the study data, in addition to descriptive statistical methods (mean, standard deviation, minimum, maximum, median frequency), Student's t-test was used for comparisons between groups of normally distributed parameters and Mann Whitney U test was used for comparisons of non-normally distributed parameters between two groups. Fisher's Exact Chi-Square test, Fisher Freeman Halton Exact Chi-square test, Continuity (Yates) Correction and Mc Nemar test were used to compare qualitative data. Kappa coefficient of agreement was calculated for the level of agreement between MR diagnosis and transvaginal ultrasound. The most appropriate cut-off point was chosen based on the ROC curve analysis. Significance was evaluated at the $p < 0.05$ level.

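### The ROC cut-off is chosen in the same 65 women with no planned correction; sensitivity and specificity reported at it under an accuracy-optimising rule would each be about 3 to 6 points too high on average

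*Combined protocol and SAP*

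**What the plan says.** The statistical analysis paragraph gives ROC analysis one sentence: "The most appropriate cut-off point was chosen based on the ROC curve analysis". It does not name the variable on the curve, the rule that defines the best point, or the accuracy measures to be reported there.

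The opening paragraph describes a single sample, "65 women between the ages of 18-52", "divided into adenomyosis (n=34) and fibroids (n=31) groups". No second or validation sample appears. The plan gives no kPa threshold fixed in advance, no split sample, cross-validation or bootstrap, and no confidence interval for an accuracy measure.

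The likely marker is the elastography reading, described as "numerical values which represent the mean stiffness value of the region of interest", because it is the only continuous index-test measure in the document. The text also says that "the minimum and maximum mean stiffness values were recorded for both study and control groups". That may only mean the range of this one variable in each group, and nothing below depends on how it is read.

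**The concern.** A cut-off picked because it performs best in a sample will tend to look better in that sample than in new women, since the choice also fits chance features of the data. With 34 and 31 women the effect is not negligible. Readers would naturally take sensitivity and specificity at the cut-off as what the threshold achieves elsewhere, although the document does not say that it is meant for clinical use.

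The consequence has two conditions: that these measures are reported at the chosen cut-off, and that the rule optimises accuracy. The plan settles neither, so a reader cannot tell whether the bias is near zero or near 6 points.

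**Working it through.** **Inputs from the document.** 34 women with adenomyosis (taken as the target condition) and 31 with fibroids; cut-off chosen from the ROC curve; no correction. The document gives no AUC, sensitivity or specificity, so there is no stated figure to reproduce.

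**Assumptions.** Normal marker with equal SDs, and true AUC 0.7, 0.8 or 0.9. The separation in SDs is d = √2·Φ⁻¹(AUC). True sensitivity and specificity at the best cut-off are then both Φ(d/2), that is 64.5%, 72.4% and 81.8%.

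**Step 1: size of the bias.** Overstatement = apparent value at the chosen cut-off minus the true value at that same cut-off, averaged over 20,000 simulated datasets per setting. J = sensitivity + specificity − 1. The Monte Carlo standard error of the J difference is at most 0.0008.

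| Rule | True AUC | Sensitivity (points) | Specificity (points) | J apparent / true | Overstatement of J |
|---|---|---|---|---|---|
| Youden | 0.7 | 5.7 | 6.2 | 0.384 / 0.265 | 0.119 |
| Youden | 0.8 | 5.0 | 5.3 | 0.527 / 0.424 | 0.104 |
| Youden | 0.9 | 4.0 | 4.4 | 0.697 / 0.613 | 0.084 |
| Closest to corner | 0.7 | 4.1 | 4.4 | 0.366 / 0.281 | 0.085 |
| Closest to corner | 0.8 | 3.7 | 4.0 | 0.514 / 0.437 | 0.077 |
| Closest to corner | 0.9 | 3.3 | 3.6 | 0.692 / 0.623 | 0.069 |
| Sensitivity nearest specificity | 0.7 | ≤ 0.6 | ≤ 0.6 | 0.290 / 0.286 | 0.004 |
| Sensitivity nearest specificity | 0.8 | ≤ 0.6 | ≤ 0.6 | 0.450 / 0.443 | 0.007 |
| Sensitivity nearest specificity | 0.9 | ≤ 0.6 | ≤ 0.6 | 0.639 / 0.628 | 0.011 |

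(Differences are taken before rounding.)

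**Step 2: robustness.** A second simulation (4,000 datasets per setting) added two more accuracy-optimising rules, overall accuracy and the product of sensitivity and specificity. Over AUC 0.70 to 0.95, all four such rules gave 2.9 to 6.1 points per measure. Youden with SD ratios from 0.5 to 2 gave 2.9 to 5.4 points. Setting sensitivity nearest specificity gave about 0 to 0.8 points. The groups are formed from examination and ultrasound, so MRI could shift the split; at an assumed 40/25 or 28/37 the Youden overstatement of J is 0.087 to 0.122.

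**Step 3: comparison with sampling error.** The half-width is 1.96·√(p(1−p)/n):
- p = 0.645: n = 34 gives 16.1 points and n = 31 gives 16.8.
- p = 0.818: n = 34 gives 13.0 points and n = 31 gives 13.6.

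At AUC 0.7, 16.1/5.7 ≈ 2.8; at AUC 0.9, 13.0/4.0 ≈ 3.3. The half-width is therefore about three times the Youden bias.

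**Step 4: what an ordinary 95% interval does.** At the Youden cut-off the true value lies below a Wilson interval in 5.5% to 8.6% of datasets, and below an exact interval in 4.5% to 6.4%, against a nominal 2.5%. It lies above the interval in 0.1% to 0.4%. Overall coverage is 91% to 94% (Wilson) or 94% to 95% (exact), so the fault is mainly one of direction.

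**Step 5: stability of the cut-off.** The 95% sampling range of the Youden cut-off spans 1.2 to 1.8 within-group SDs.

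**Step 6: does correction help?** Bootstrap optimism correction was run on 2,000 datasets with 200 resamples each. J is shown as apparent / true / corrected, at AUC 0.7, 0.8 and 0.9:
- Youden: 0.379/0.264/0.300, 0.527/0.425/0.458, 0.700/0.613/0.643. Optimism removed: 69%, 68%, 65%.
- Closest to corner: 0.364/0.281/0.305, 0.516/0.437/0.462, 0.690/0.622/0.645. Optimism removed: 71%, 68%, 67%.

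Root mean squared error of J falls from 0.147 to 0.111, 0.137 to 0.108 and 0.119 to 0.097 under Youden. Under closest-to-corner it falls from 0.135 to 0.117, 0.126 to 0.109 and 0.108 to 0.094.

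**The case against.** The strongest reply is that nothing in the plan is shown to be wrong. One sentence mentions ROC. It names no rule and does not promise sensitivity or specificity, and its wording fits a rule under which the bias is negligible. The firm defect would then be only that rule and variable are undisclosed. This stands as a limit on the claim: the bias is conditional.

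The size also rests on an assumed AUC. Values near 6 points need a Youden-type rule, an AUC near 0.7 and similar SDs; unequal SDs lower the top of the range, and at AUC 0.98 the Youden figure is 2.8 to 2.9 points. This stands too, but the direction is the same under every accuracy-optimising rule examined.

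Third, sampling error dominates. Under Youden the apparent value of a measure is still below the true one in 20% to 25% of datasets, and exact intervals keep nearly nominal coverage. That is correct, but an interval centred on an inflated estimate does not show the reader which way it leans.

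Finally, the bootstrap leaves about 1 to 2 points per measure uncorrected, and lowers the root mean squared error of each measure only from 0.075–0.095 to 0.067–0.080 under Youden. The gain is modest, but so is the cost.

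**Conclusion.** The concern holds as a conditional one. The cut-off is data-driven, the plan describes one sample of 65 women, and no correction is planned. If sensitivity and specificity are reported at the cut-off and the rule optimises accuracy, each is overstated by about 3 to 6 points on average, and J by 0.069 to 0.119. This assumes a 34/31 split, a roughly normal marker with equal SDs and a true AUC of 0.7 to 0.9. If sensitivity was set nearest specificity, the overstatement is under 1 point. This is a worthwhile, inexpensive improvement to the analysis, not a demonstrated error in it.

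**What to change.** - State which stiffness value went into the ROC analysis and which rule selected the cut-off. The choice has already been made, so this is disclosure, not prespecification.
- Report the AUC with a 95% CI.
- Report bootstrap optimism-corrected sensitivity and specificity beside the apparent values. Repeat the cut-off selection in each resample, along with any choice between stiffness values if one was made.
- Give a bootstrap interval for the cut-off. In simulation the 95% percentile interval covered the optimal cut-off in 93% to 96% of datasets under Youden and closest-to-corner.
- Label the cut-off exploratory until it has been validated in new patients.

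The cost is a short script and somewhat less favourable figures, with no new patients. The elastography paragraph says that "All images and data were saved in the memory of the ultrasound device for further evaluation and processing"; this refers to the device memory, but the per-woman values already analysed are all that the script needs. If the rule was sensitivity nearest specificity, the correction changes almost nothing (root mean squared error of J 0.120 to 0.119, 0.114 to 0.112 and 0.099 to 0.098 at AUC 0.7, 0.8 and 0.9), so running it does no harm.
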